8. DATA MANAGEMENT

- For this study subject data will be entered into GSK defined eCRFs, transmitted electronically to GSK or designee and combined with data provided from other sources in a validated data system.
- Management of clinical data will be performed in accordance with applicable GSK standards and data cleaning procedures to ensure the integrity of the data, e.g., removing errors and inconsistencies in the data.
- Adverse events and concomitant medications terms will be coded using MedDRA (Medical Dictionary for Regulatory Activities) and an internal validated medication dictionary, GSKDrug.
- eCRFs (including queries and audit trails) will be retained by GSK, and copies will be sent to the investigator to maintain as the investigator copy. Subject initials will not be collected or transmitted to GSK according to GSK policy.

9. STATISTICAL CONSIDERATIONS AND DATA ANALYSES

9.1. Hypotheses

The goal of the study is to assess the efficacy of twice daily 15 mg and 50 mg FBE IV DNX given with standard of care 75 mg oseltamivir twice daily, in hospitalized patients with influenza. The primary endpoint is the TTCR in subjects with confirmed influenza. TTCR and Clinical response is defined in Section 9.4.1.

A probability inference approach will be used for decision-making. A Bayesian predictive probability of success will be provided to support assessment of early stopping for futility and/or efficacy and for final efficacy. Observed data at interim analyses or final analysis of this study will be used to calculate predictive probability of success of a future study with larger sample size. Success is defined as a statistically significant treatment effect (p -value <0.025 for hazard ratio of TTCR >1) in a future two-arm comparative superiority study with 300 subjects per arm.

9.2. Sample Size Considerations

9.2.1. Sample Size Assumptions

The TTCR endpoint was used in GSK Study NAI14373 (IV zanamivir), conducted in a similar population of hospitalized influenza subjects. The TTCR endpoint from NAI14373 was calculated as defined in the protocol. Median TTCR from Kaplan-Meier estimates in the oseltamivir treatment group from the confirmed influenza population are summarized (Table 8), and applied to the less severe subjects and for critically ill subjects at baseline separately. Hazard ratio estimates from the proportional hazard model of IV zanamivir vs oseltamivir range from 1.6 – 1.7 in the Mechanical ventilation at baseline sub-group in study NAI14373. Hazard ratio and clinical improvement in days over oseltamivir are provided in the table for reference.

Table 8 Hazard Ratio and Clinical Improvement over oseltamivir

Population	Median Recovery time (days)	Hazard Ratio	Clinical effect Improvement in Days
Less severe sub-population	5.8	1.2	1
		1.5	2
Critically ill sub-population	20.1	1.2	3.4
		1.5	6.7

TTCR is assumed to follow exponential distribution with constant hazard rate λ . To incorporate prior information on the oseltamivir arm, a weak informative prior of Gamma (4, 4/0.83) distribution with mean parameter of 0.83 and weight parameter of 4, will be used for λ in the oseltamivir arm. The mean and median hazard rates for the Gamma distribution are 0.83 and 0.76, respectively, with 2.5th percentile of 0.226 and 97.5th percentile of 1.819. A constant hazard rate of 0.83 for exponential distribution centers the recovery time at 5.8 days. A weight parameter of 4 provides relative small weight on the prior and will allow data to dominate the posterior, the 95% recovery time could range from 2.6 to 21.4 days to allow wide range possible outcomes. A non-informative prior will be used for DNX arms.

The sample size of 300 was selected based on simulations to achieve at least 80% overall power under assumption of HR =1.5 for 50 mg of DNX FBE and HR =1.2 for 15 mg of DNX FBE and keep type I error less than 10% under no-effect assumption.

The study will enrol approximately 300 subjects with ratio 2:2:1 to 15mg IV DNX FBE+ OSV, 50mg IV DNX FBE + OSV and IV DNX placebo +OSV arms. An informative prior on the oseltamivir arm for the Bayesian analysis provides additional data from prior study for the control arms, combining prior data and data from this study allows us to have fewer subjects on the control arm with a 2:2:1 randomization ratio.

It is assumed that there is no difference in treatment effect between the less severe and severe population. Assuming a treatment effect of HR =1.5 for 50 mg of DNX FBE and

a clinically meaningful treatment effect of HR =1.2 for 15 mg of DNX FBE, there is an 82% chance that at least one dose will meet the success criteria described below:

At interim: Probability (success) >90%

Final: Probability (success) >50%

Assuming a HR of 1 for both doses, the overall type I error is 9%, i.e. there is a 9% chance of one or more doses being declared success incorrectly.

Table 9 Type I error by Interim and Overall

Hazard ratio	Type I error for Interim 1 n=100	Type I error for Interim 2 n=200	Overall Type I Error
Criteria	Probability (success) >90%	Probability (success) >90%	Probability (success) >50%
L: HR=1 H: HR=1	1%	0%	9%

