12.9.2. Statistical Modeling

At each interim analysis and at the final analysis, the TTCR data will be analyzed with independent dose-response models. The adaptation will be based on the predictive probability of success.

12.9.2.1. Hazard Model:

Let T_0 be the time to clinical response for the control arm with exponential distribution

$$T_0 \sim \text{Exp}(\lambda)$$

Where λ is the hazard rate constant of subjects in the control arm, the parameter is modeled as:

$$\lambda \sim \text{Gamma}\left(n, \frac{n}{\mu}\right)$$

Where n is prior weight parameter and μ is prior mean parameter, we set $n=4$ and $\mu=0.83$ based on the hazard rate observed in study NAI114373.

And T_d be the time to clinical response for the dose level d :

$$T_d \sim \text{Exp}(h_d)$$

where $h_d = \lambda e^{\theta_d}$, and θ_d is log-hazard ratio.

12.9.2.2. The dose –response Model:

Independent dose-response model estimate the response for each arm separately with normal distribution.

$$\theta_d \sim N(\mu_d, \nu_d^2)$$

Where θ_d is log-hazard ratio compared to control arm on the treatment arm d . The two dose levels considered are $d=1$ (15 mg BID), and $d=2$ (50 mg BID). μ_d is the mean of dose d and ν_d^2 is the variance of dose d . The same non-informative prior $N(0,1)$ is used for all doses of the dose-response model.

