12.9.5. Probability of success

Probability of success, denoted $\text{Prob}(\text{Success})$, will be used to evaluate futility, arm dropping and early success. Success is defined as a statistically significant treatment effect ($p\text{-value} < 0.025$ for hazard ratio of $\text{TTCR} > 1$) in a two-arm comparative superiority study with 300 subjects per arm, given observed data at interim and final analyses.

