12.9.10. Simulation Scenarios

In order to characterize and understand the performance of the design, we simulated the trial under several different scenarios.

Scenarios considered for the true hazard ratios for low dose and high dose DNX are shown in [Table 11](#).

Table 11 Dose- Response profile for Hazard Ratio

	DNX 15mg + OSV	DNX 50mg + OSV
1. No effect	1	1
2. Small effect	1.2	1.2
3. Large effect	1.5	1.5
4. Mixed effect	1.2	1.5
5. High dose large effect	1	1.5

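### The design pools one control hazard over two severity groups with medians of 5.8 and 20.1 days; at those medians the stated 82% power is about 60–71%

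*Protocol*

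**What the plan says.** Protocol 9.2.1 takes oseltamivir-arm medians from an earlier study of IV zanamivir, "applied to the less severe subjects and for critically ill subjects at baseline separately". Table 8 lists 5.8 days for the less severe and 20.1 days for the critically ill. Sections 4.1.1 and 4.1.2 open enrolment to critically ill subjects after a safety review of about 30 less severe ones.

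The same section then states: "TTCR is assumed to follow exponential distribution with constant hazard rate". The control prior is Gamma(4, 4/0.83), and "A constant hazard rate of 0.83 for exponential distribution centers the recovery time at 5.8 days". Sections 9.4.1.1 and 12.9.2.1 carry this into the primary model, where one λ "is the hazard rate constant of subjects in the control arm", with no severity term. Severity appears only as a Kaplan-Meier subgroup (9.4.1.3) and is not among the minimisation factors (6.2).

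The sample size was chosen to give at least 80% power and "keep type I error less than 10% under no-effect assumption". For hazard ratios of 1.2 and 1.5, "there is an 82% chance that at least one dose will meet the success criteria described below". Section 12.9.10 introduces the simulation grid with "Scenarios considered for the true hazard ratios for low dose and high dose DNX are shown in" Table 11. Nothing but the hazard ratios varies across it.

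**The concern.** The two medians imply control hazards that differ 3.5-fold (20.1/5.8). A mixture of two such exponentials is not exponential. A single-rate model fitted to it treats the log hazard ratio as more precise than it is. The prior also sits on the faster group, so it pulls the estimated control rate up and the estimated benefit down. The prior counts as about 4 events against roughly 20 control subjects at the first interim.

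The operating characteristics in Table 12 justify N = 300 and the decision thresholds. If they hold only when every subject recovers like a less severe one, the stated power does not describe the population the trial sets out to enrol.

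**Working it through.** **Inputs from the protocol.** Medians 5.8 and 20.1 days (Table 8); hazard ratios 1.2 and 1.5, equal in both severity groups (9.2.1); allocation 1:2:2, with a dropped arm's places not reallocated (12.9.3); looks at 100, 200 and 300; follow-up to Day 45. A dose is dropped, or the study stopped for futility, below 0.3; early success is above 0.9 and final success above 0.5 (12.9.6 to 12.9.9).

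**Assumed or inferred.** The critically ill share (5% to 50%) is assumed. The number of future events E is inferred: 12.9.5 speaks only of a "two-arm comparative superiority study with 300 subjects per arm, given observed data at interim and final analyses".

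**Formulas.**
- Weekly hazard = 7 ln2 / median: 7 × 0.693/5.8 = 0.837 and 7 × 0.693/20.1 = 0.241. The prior mean of 0.83 is therefore weekly: 7 × 0.693/0.83 = 5.85 days.
- With posterior mean m and variance v for a dose's log hazard ratio (Laplace approximation), Prob(success) = Φ[(m/s − 1.96)/√(1 + v/s²)], where s² = 4/E.
- For E = 300, s = √(4/300) = 0.1155, so final success needs m > 1.96 × 0.1155 = 0.226.

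Times are exponential within stratum and censored at Day 45. There were 40,000 simulated trials per cell (20,000 for the Table 12 check and the 600-event runs), with Monte Carlo SE of 0.15 to 0.35 points.

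**Reproducing Table 12** (all subjects at 5.8 days, E = 300):

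| Scenario | 1 | 2 | 3 | 4 | 5 |
|---|---|---|---|---|---|
| Success, computed | 8.3% | 44.0% | 90.2% | 81.7% | 81.2% |
| Success, stated | 9% | 45% | 90% | 82% | 81% |
| Mean N, computed | 157 | 207 | 209 | 205 | 187 |
| Mean N, stated | 160 | 208 | 208 | 207 | 191 |

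With E = 600 (300 per arm, all with events), scenario 4 power is about 91% and type I error about 19%, which do not match. Hence the 300-event inference.

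**Protocol model in a mix at the Table 8 medians** (E = 300, hazard ratios 1.2/1.5 in both strata). The pooled control rate is Σw(1−e^(−λc)) / Σ[w(1−e^(−λc))/λ] with c = 45/7 weeks. At a 10% share this is (0.9×0.995 + 0.1×0.788)/(0.9×1.190 + 0.1×3.265) = 0.70.

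| Critically ill | Pooled control rate/week | Power | Type I error |
|---|---|---|---|
| 0% | 0.84 | 82% | 8.6% |
| 5% | 0.76 | 76% | 10.2% |
| 10% | 0.70 | 71% | 10.5% |
| 20% | 0.59 | 66% | 10.6% |
| 30% | 0.52 | 62% | 10.2% |
| 50% | 0.40 | 60% | 8.8% |

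Replacing the Laplace step by numerical integration (6,000 trials per cell) gives power of 71.9/66.9/64.1/60.9% and type I error of 10.5/11.6/10.6/8.7% at 10/20/30/50%.

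**Where the loss comes from.** Recentring the single prior on the pooled rate gives power of 75/72/71/71% at 10/20/30/50%, with type I error of 12–14%. At 10%, then, 82 − 75 = 7 points go to pooling and 75 − 71 = 4 to prior centring; at 50%, 82 − 71 = 11 and 71 − 60 = 11. With near-zero prior weight, power is 79% in the homogeneous case and 72/68/68% in the mix at 10/30/50%, so pooling costs power without any prior pull.

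**Dependence on the interim rules.** In scenario 4 the chance of crossing the first futility threshold rises from 8% to 14/17/20/23% at 10/20/30/50%. These are crossing rates, not stopping rates. If futility stops and arm drops are never applied, power still falls, from 87% to 80/74/72% at 10/30/50%.

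**Sensitivity**, shares 5/10/20/30/50%:
- Critically ill median 15 days: power 78/75/71/69/66%. At 10 days: 81/80/78/76/74%.
- First 30 subjects all less severe: 76/73/67/64/61%.
- E = 600: power falls from 91% to 86/82/77/74/72%, with type I error of 17–20%.

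**The case against.** The strongest reply is that the loss rests on inputs the documents do not give. The severity share is nowhere stated, the event count is back-solved, and the documents do not say which control population was simulated. If the critically ill median were 10 days, little power would be lost at small shares. Exponential times within each stratum are a further assumption: with Weibull shapes of 0.8 and 1.2, power at a 10% share is 77% and 64%, against 84% and 78% in a homogeneous population. Death and dropout are not modelled. All of this stands as a condition on the size. It does not supply a mix under which the stated figures hold at the protocol's own medians.

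Second, pooling is not the whole cause. That is right: prior centring accounts for about a third of the loss at a 10% share (4 of 11 points) and half at 50%. A related point also stands. At the 0.5 threshold the posterior variance cancels, so understated variance does not in itself lower final power. What changes is that m falls and its true spread grows. For the 50 mg dose the mean of m goes from 0.388 to 0.357 and 0.322 at 10% and 30%, and its sampling SD from 0.152 to 0.183 and 0.191.

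Third, the protocol offers partial safeguards. Its wide prior (2.6 to 21.4 days) expresses uncertainty about one common rate, not a mixture. The equal-effect assumption concerns hazard ratios, not baseline hazards. The severity subgroup does not feed Prob(success). The decision rule is only supportive (4.1, 12.9.4), but the loss remains when futility stopping is removed.

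Finally, nothing downstream is affected. The trial ended after 10 subjects, and the SAP has no hypothesis test, interim analysis or model (SAP 2.1, 2.4, 3.1, 7.1.2). This stands and limits the scope of the point.

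**Conclusion.** The point holds for the protocol design. The stated 82% power and 9% type I error describe a single 5.8-day population. At the protocol's own medians, power is about 71% with 10% critically ill and about 60% with 50%. Type I error is slightly above the 10% limit at shares of 5% to 30%.

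These sizes assume the Table 8 medians, exponential times within stratum, the same hazard ratios in both strata and 300 future events. The 80% target is already missed at a 5% share (76%). The loss shrinks if the critically ill recover faster than Table 8 says. It should be fixed in any reuse of the design; confidence in the exact size is medium.

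**What to change.** - **Model.** In 9.4.1.1 and 12.9.2.1, give each baseline severity stratum its own control hazard and keep one log hazard ratio per dose. Use the 9.4.1.3 definition, which matches the critically ill criteria in 4.3. The opening paragraph of 4.3 uses a broader list that includes renal failure and sepsis, so state which definition produced the 20.1-day median.
- **Priors.** Centre them on the two Table 8 medians and hold the total weight at 4, for example 3.5 + 0.5. The small critically ill weight guards against mis-centring, which can raise type I error.
- **Simulation.** Re-run Table 12 over stated severity mixes and critically ill medians, state the number of future events, and restate power and type I error.
- **Threshold.** With weights 3.5 + 0.5 and shares of 5–50% at 20.1 days, a final threshold of 0.50 gives 81–82% power and 8.7–10.3% type I error; 0.52 gives 80–81% and 8.0–9.3%. Over true critically ill medians of 10 to 30 days, 0.52 gives 79–83% and 7.7–9.9%. The 9.9% lies within simulation error of the limit, so the sponsor should retune the threshold in its own runs.

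Recentring the single prior is not enough, because type I error is then 12–14%. Adding severity to the minimisation is optional.

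**Cost.** One extra parameter, a simulation re-run and about 1 point of power at 0.52; no added patients or assessments. If nobody is critically ill, the stratified model at 0.50 gives 81% power and 8.7% type I error. The protocol does not say whether its simulation software can fit stratum-specific hazards, so that needs checking.

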9.2.3. Sample Size Re-estimation or Adjustment

No sample size re-estimation is planned.

An adaptive design is employed that allows for dropping a dose at interim analyses. These interim analyses also allow for early stopping for futility or efficacy. The target

sample size is 300 subjects; if early futility or efficacy criteria are met, as few as 75-100 subjects may be enrolled. The first interim analyses will occur after the first flu season if there are more than 75 subjects enrolled. Additional interim analyses may be performed after approximately 50-66% of subjects have been enrolled.

Assuming an effective drug (HR = 1.2 and 1.5 for low and high dose respectively), there is 26% probability, the sample size is 100 subjects at the end of the study, and 67% probability the sample is less than 220. Assuming an ineffective drug (HR =1 for both doses), there is 47% probability, the sample size is 100 subjects at the end of the study, and 86% probability the sample is less than 220. Average sample size for each Dose-response profile is provided in [Appendix 9](#).

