9.4. Key Elements of Analysis Plan

9.4.1. Efficacy

9.4.1.1. Primary Analysis

Probability of success, denoted Prob(Success), will be calculated. Success is defined as a statistically significant treatment effect (p-value<0.025 for hazard ratio of TTCR >1) in a future two-arm comparative superiority study with 300 subjects per arm, given observed data.

Let T_0 be the time to clinical response for the control arm with exponential distribution

$$T_0 \sim \text{Exp}(\lambda)$$

Where λ is the hazard rate constant of subjects in the control arm, the parameter is modeled as:

$$\lambda \sim \text{Gamma}\left(n, \frac{n}{\mu}\right)$$

Where n is prior weight parameter and μ is prior mean parameter, we set n=4 and $\mu=0.83$ based on the hazard rate observed in study NAI114373.

Let T_d be the time to clinical response for the dose level d :

$$T_d \sim \text{Exp}(h_d)$$

where $h_d = \lambda e^{\theta_d}$, and θ_d is log-hazard ratio and modeled with independent dose-dose response model.

Kaplan-Meier estimates for the median of TTCR for each treatment group and the median difference and 95% confidence interval (CI) between DNX arms and OSV will be provided.

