12.9.11. Operating Characteristics

[figure not shown]
[Table 12](#) shows the operating characteristics for different scenarios by interim analysis and final analysis. [Figure 1](#) and [Figure 2](#) show the possible sample size, corresponding probability of the sample size and cumulative probability of sample size under two selected scenarios.

Table 12 Operating Characteristics by Interim of Selected Scenarios

Scenario	Hazard ratio	Interim 1 n=100				Interim 2 n=200				Final	Average Sample size
		P(drop low dose)	P(drop high dose)	P(stop study for futility) (Observed HR 0.85 – 1.2)	P(stop study for efficacy) (Observed HR 1.5 – 3.2)	P(drop low dose)	P(drop high dose)	P(stop study for futility) (Observed HR 1 – 1.15)	P(stop study for efficacy) (Observed HR 1.55 – 2.7)		
1. No effect	L: HR=1 H: HR=1	15%	19%	46%	1%	2%	3%	25%	0%	9%	160
2. Small effect	L: HR=1.2 H: HR=1.2	16%	15%	22%	5%	4%	5%	10%	3%	45%	208
3. Large effect	L: HR=1.5 H: HR=1.5	7%	8%	4%	26%	1%	1%	2%	19%	90%	208
4. Mixed effect	L: HR=1.2 H: HR=1.5	31%	2%	8%	18%	8%	0%	3%	13%	82%	207
5. High dose large effect	L: HR=1 H: HR=1.5	54%	1%	10%	18%	12%	0%	3%	12%	81%	191

Futility rule at Interim: Drop dose: Prob(success) for the dose < 30%, Stop study for futility: Prob(success) for best dose< 30%, Stop study for efficacy: Prob(success) for best dose> 90%; Final success criteria: Prob(success) for best dose>50%
Success is defined one side $p \leq 0.025$ in a two arm superiority study with $n=300$ per arm.

Figure 4 Sample Size Distribution for an effective drug and an ineffective drug

Location of brown line on x-axis shows possible study sample size, height of brown line shows probability of the sample size, and blue line shows the cumulative probability of study sample size. Top panel shows an example of an ineffective drug with HR =1 for both doses; the bottom panel shows an example of an effective drug with HR =1.2 for low dose and HR=1.5 for high dose.

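### The protocol's 9% type I error and 82% power do not follow from its success rule of a future study with 300 subjects per arm; at its own control hazard that rule gives about 18% and 91%, above its 10% limit

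*Protocol*

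**What the plan says.** Success is a one-sided p<0.025 for the TTCR hazard ratio in a hypothetical later trial. Protocol Section 9.4.1.1 sets that trial as "in a future two-arm comparative superiority study with 300 subjects per arm, given observed data". Appendix 9, Section 12.9.5 repeats "in a two-arm comparative superiority study with 300 subjects per arm", and the footnote to Table 12 has "in a two arm superiority study with $n=300$ per arm". The synopsis and Section 9.1 agree.

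All decisions use the probability of this success: drop an arm or stop for futility below 30%, stop for efficacy above 90%, and declare final success above 50% (Section 9.2.1; Sections 12.9.6 to 12.9.9).

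Section 9.2.1 says N=300 was chosen by simulation for at least 80% power and to "keep type I error less than 10% under no-effect assumption". It then reports 82% power for hazard ratios of 1.2 (15 mg) and 1.5 (50 mg), and: "Assuming a HR of 1 for both doses, the overall type I error is 9" percent. On the control arm it says: "A constant hazard rate of 0.83 for exponential distribution centers the recovery time at 5.8 days".

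Section 9.2.3 adds sample-size probabilities. For an ineffective drug "there is 47% probability, the sample size is 100 subjects at the end of the study"; for the 1.2/1.5 scenario "there is 26% probability, the sample size is 100 subjects at the end of the study".

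**The concern.** A predictive-probability rule is only as strict as the future trial it refers to. The larger that trial, the smaller the observed effect needed to predict its success, and the more often an inactive dose passes. With 300 per arm and nearly complete events, the final rule needs an estimated hazard ratio of only about 1.17. Two doses each get up to three looks, the control arm has at most 60 subjects, and the priors are weak. A 9% overall false-success rate looked too low for that bar.

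At stake is the design justification. If the written rule is the intended one, the protocol understates its false-success rate by about half and misses its own limit. If the published figures are right, the rule is misdescribed in five places.

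**Working it through.** **Inputs from the protocol**
- Control hazard 0.83, median 5.8 days (9.2.1). Since ln2/0.83 = 0.835, and 0.835 weeks is 5.85 days, the unit is per week.
- Follow-up to Day 45 (4.2).
- Priors: Gamma(4, 4/0.83) on the control hazard (9.2.1); N(0,1) on each log hazard ratio (12.9.2.2).
- Looks at 100, 200 and 300; allocation 1:2:2, so 20/40/40 per hundred; a dropped arm is not replaced (12.9.3, Table 12).
- Thresholds as above.

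**Prior check.** The Gamma prior's 2.5th percentile, median and 97.5th percentile come out at 0.226, 0.76 and 1.819, as published.

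**Future events.** P(event by Day 45) = 1 − exp(−0.83 × 45/7) = 0.995. With 300 per arm, E = 600 × 0.995 ≈ 597. With 300 in total, E ≈ 299. Applying 45-day follow-up to the future study is an assumption.

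**Decision quantity.** With m and v the posterior mean and variance of a log hazard ratio, and s = √(4/E):

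Prob(success) = Φ((m − 1.96s)/√(v + s²)), which exceeds 50% when m > 1.96s.

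**Hand check** (every subject an event, priors ignored). The SE of one log hazard ratio at 120 versus 60 events is √(1/120 + 1/60) = 0.158.
- 300 per arm: 1.96 × √(4/600) = 0.160, HR 1.17. One null dose at one look passes with probability 1 − Φ(0.160/0.158) = 15.6%.
- 150 per arm: 1.96 × √(4/300) = 0.226, HR 1.25. The same chance is 7.6%.

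**Simulation of the full design.** 40,000 trials per scenario; exponential TTCR; censoring at Day 45; complete follow-up at each look. Simulation error on success rates is about 0.2 points. Cells show published / 597 events / 299 events.

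| HR 15 mg, 50 mg | Success % | Average N | Interim-1 efficacy stop % | Interim-1 futility stop % |
|---|---|---|---|---|
| 1, 1 | 9 / 18 / 9 | 160 / 174 / 157 | 1 / 3 / 1 | 46 / 39 / 50 |
| 1.2, 1.2 | 45 / 62 / 43 | 208 / 212 / 206 | 5 / 12 / 6 | 22 / 14 / 22 |
| 1.5, 1.5 | 90 / 95 / 90 | 208 / 183 / 209 | 26 / 42 / 27 | 4 / 2 / 4 |
| 1.2, 1.5 | 82 / 91 / 82 | 207 / 189 / 204 | 18 / 32 / 20 | 8 / 5 / 8 |
| 1, 1.5 | 81 / 89 / 81 | 191 / 175 / 188 | 18 / 30 / 19 | 10 / 6 / 9 |

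**Section 9.2.3 probabilities**, same order:
- Null: P(N=100) 47 / 41 / 51%; P(N up to 220) 86 / 79 / 86%.
- 1.2/1.5 scenario: P(N=100) 26 / 36 / 28%; P(N up to 220) 67 / 73 / 67%.

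The 220 limit is read as inclusive. Read strictly, the 299-event values are 72% and 43%.

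A separate calculation by numerical quadrature gave 19.1% and 91.2% for 300 per arm, and 8.8% and 82.4% for 150 per arm.

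**Sensitivity to what is not stated**
- Null success by future events, at 0.83 per week: 597, 18%; 420, 13%; 350, 10%; 299, 9%.
- Share critically ill, applied to both trials at 300 per arm (null success / power at 1.2, 1.5): 0%, 18/91; 20%, 19/77; 50%, 15/70; 100%, 9/72. The critically ill hazard is ln2/(20.1/7) per week, with 79% events by Day 45. The all-critically-ill case meets the 10% limit but gives 62% null futility at interim 1, against 46% published.
- At 300 per arm, changes to the control prior, look times, critical z, arm dropping, dropout or log-HR prior gave 14% to 19% false success. None gave 9% and 82% together.

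**The case against.** The documents fix the number of future subjects, not events. Day 45 is this study's follow-up; nothing states the follow-up, event fraction or case mix of the hypothetical trial. With 300 per arm and half of subjects having events, the results are 9% and 81%, so the published figures are not impossible under the written rule. This stands as a condition on the result. But a 50% event fraction is hard to square with the protocol's own hazard and follow-up, and it is stated nowhere. The severity mixes were not crossed with a different future follow-up.

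The 300-in-total explanation is also imperfect. Null futility comes out at 50% and 21% at the two interims, against 46% and 25% published. Table 12 prints observed hazard ratios at efficacy stops starting at 1.5 and 1.55; with 299 events the lowest simulated values were about 1.67 and 1.64, and with 597 events 1.53 and 1.47. The futility ranges lean the other way: upper bounds of 1.2 and 1.15 are printed, against 1.16 and 1.15 (299 events) and 1.06 and 1.08 (597). Table 12 does not define the observed hazard ratio, and neither input reproduces every range, so some other modelling difference is possible. The explanation is therefore inference only.

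Finally, the SAP (Sections 2.1, 2.4 and 3.1) tests no hypothesis and plans no formal interim analysis after termination at 10 subjects. That limits the practical consequence; it does not make the published figures correct.

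**Conclusion.** The concern holds. With 300 per arm, a control hazard of 0.83 per week and 45-day follow-up in both trials, false success is about 18%, twice the stated 9% and above the protocol's 10% limit. Power is about 91%, not 82%. Null early stopping for efficacy, both interims combined, is about 3.6% rather than 1%. The mismatch is well established under near-complete future events; its cause is not, because the FACTS input is not available. This is an error in the design justification that should be fixed, with no effect on the descriptive results.

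**What to change.** Check what was entered in FACTS for the future study, then make rule and figures agree.

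- **If 300 in total was simulated and intended:** correct the per-arm wording in the synopsis, 9.1, 9.4.1.1, 12.9.5 and the Table 12 footnote. The operating characteristics can then stand, subject to checking the printed observed-HR ranges against the simulation output.
- **If 300 per arm is intended:** state the future study's event count, follow-up and severity mix. Re-run, restate Tables 9 and 12, Figure 4 and the 9.2.3 probabilities, and recalibrate the final threshold to the 10% limit. As an illustration at 0.83 per week only, a final threshold of 65% gives 10.3% type I error and 85% power; 70% gives about 8% to 9% and 82% to 83%.

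The cost is one check of the input, then either a wording correction or one re-run with a recalibrated threshold. No extra patients are needed.
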